5.0 ENROLLMENT

The patients at the top of the adult kidney transplant list awaiting DDKT maintained by UIHHSS Transplant will be used to screen for eligibility. See addendum for Eligibility Checklist. Study personnel will perform the screening. A password protected Microsoft Excel sheet will be provided by the Transplant team at UIHHSS. This sheet will have the MRN for the top patients on the kidney transplant list. If patients are initially eligible via inclusion and exclusion review, they will remain on the password protected Microsoft Excel sheet. If they are not eligible, they will be removed after screening by one of the study personnel. This password protected Microsoft Excel sheet will be maintained on the "H" drive behind the University firewall maintained by the CCTS. It is estimated that 40 subjects will be consented/enrolled in order for 20 patients to receive study drug. Twenty patients are the goal for this study and no more than 20 patients will receive study drug.

All eligible study subjects will receive a Research Letter (see addendum for Research Letter) via the mail. One week after the Research Letter is mailed, the subjects that have not called the primary investigator regarding the study will be called via telephone by study personnel to follow-up and provide any additional information regarding the study. This call is to provide information regarding the study, study enrollment criteria, and answer any questions regarding the study. This call is informational only.

If a kidney transplant is offered to the previously contacted subjects the study personnel will be contacted by the Transplant Coordinator when the kidney transplant is confirmed. Once that subject arrives at UI Health for their transplant, subjects will be approached by study investigators in-person, reminded of the study criteria, have ample time to review study information again and the informed consent document, and will be asked to provide signed consent after the appropriate informed consent process is completed. Researchers participating in the consent process will review the informed consent document (ICD) with the recruited subject in its entirety ensuring the subject understands the research purpose, all risks/benefits and the study components of this research.

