6.0 STUDY DESIGN AND PROCEDURES

This will be a single-center, prospective, observational study.

The prospective, observational study will include 20 consecutive patients receiving DDKT requiring intraoperative or postoperative vasopressors to assess the hemodynamic efficacy and safety and efficacy of Ang II (Giapreza).

The care process for this study of Ang II (Giapreza) in deceased donor kidney transplants (DDKT) at University of Illinois Hospital and Health Sciences (UIHHSS) will follow the exact same procedure as described above except (in bold and red):

PRE-TRANSPLANT – n/a DURING TRANSPLANT

- The transplant operation begins.
- If intraoperative hypotension occurs (e.g. SBP < 120 mmHg) the attending surgeon and attending anesthesiologist will:
 - Give blood products first if patient bleeding
 - If not bleeding or hypotensive despite blood products, intravenous fluids will be given
 - If hypotensive despite intravenous fluids then the attending surgeon and attending anesthesiologist will assess for cardiogenic shock and if suspected give inotropes
 - If not in cardiogenic shock and hypotensive despite fluids (+/- inotropes) then Ang II (Giapreza) will be initiated as the first vasopressor given for the treatment of distributive shock.
 - Ang II (Giapreza) will be titrated intraoperative to achieve goal BP.
 - Ang II (Giapreza) will be initiated following the FDA approved dosing in the package insert. This dosing includes a starting dose of 20 nanograms ng/kg/min. Titration will occur every 5 minutes by increments of up to 5 ng/kg/min as needed. During the first 3 hours, the maximum dose will not exceed 80 ng/kg/min. Maintenance dose will n exceed 40 ng/kg/min. Administration through a central venous line will be recommended.
 - If the maximum dose of AT II (Giapreza) is reached (80 ng/kg/min in the first 3 hours or 40 ng/kg/min thereafter), additional vasopressor selection and management will be at the discretion of the attending surgeon and attending anesthesiologist.
 - If additional vasopressors are needed beyond Ang II (Giapreza), all other vasopressors will be titrated off first.
 - If the patient is unable to be titrated off the Ang II (Giapreza) intraoperatively, they will be continued postoperatively in the Intensive Care Unit (ICU) and titrated until the patients' blood pressure is stable without vasopressor support.
- If distributive shock does NOT occur intraoperatively, Ang II (Giapreza) will NOT be initiated.

AFTER TRANSPLANT

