Patients will be monitored according to standard monitoring for patients in the peri-operative transplant and collection of ADE will focus on those found in clinical studies using Ang II (Giapreza). The safety endpoints that will be captured will include: incidence of intraoperative arrhythmias for those who receive study drug intraoperatively (confirmed via EKG, flowsheet, or note documentation), incidence of postoperative arrhythmias occurring while receiving study drug postoperatively (confirmed via EKG, flowsheet, or note documentation), incidence of digital or other peripheral/visceral ischemia occurring during hospitalization for kidney transplant (as noted in chart documentation), incidence of venous or arterial thrombosis occurring during the hospitalization for kidney transplant (captured by ultrasound or other diagnostic imaging), incidence of thrombocytopenia while receiving study drug (as defined as platelet count < 50,000), incidence of post-operative fungal infections prior to discharge (as documented by the clinical care team), incidence of delirium while receiving study drug (as documented by the clinical care team), incidence of insulin infusion utilization while receiving study drug, pH values in the ICU at 24hrs, 48hrs, and 72hrs (if available). All of the noted safety variables above are routinely monitored for as part of ICU care.

Data Management

All patients that provide informed consent and receive Ang II (Giapreza) will have their data extracted. These patients will be considered included and associated with an alpha-numeric code that is linked to their medical record number (MRN). This list will be kept in a password protected Excel file on the primary investigator's computer stored on the H drive behind the University firewall on the primary investigator's password protected computer in a locked office. It will be available only to the co-investigators. Lastly, all data collected will not contain PHI and will be stored in Redcap.

All patients that provide informed consent but DO NOT receive Ang II (Giapreza) will be considered a screening failure and NO data will be extracted and they will not be associated with an alpha-numeric code linked to their MRN.

Records retention:

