8.0 DATA COLLECTION AND MANAGEMENT PROCEDURES

Subjects will be screened for eligibility by the study personnel. The investigators will review a list of kidney transplant patients maintained by the Transplant Coordinators for inclusion in the study. This list will be password protected and stored on the H drive behind the University firewall on the primary investigator's password protected computer in a locked office. If a subject is not eligible after reviewing inclusion and exclusion criteria, they will be removed from this list. All subjects that provide informed consent to receive Ang II (Giapreza) will remain on this list. If a subject is enrolled and receives Ang II (Giapreza), their de-identified data will be extracted and collected in Redcap. Additionally, they will be associated with an alpha-numeric code that is linked to their medical record number (MRN) and placed on a Study Subject list. This Study Subject list will be kept in a password protected Excel file on the primary investigator's computer stored on the H drive behind the University firewall on the primary investigator's password protected computer in a locked office. It will be available only to the coinvestigators and research personnel. If a subject is enrolled and does not require Ang II (Giapreza) they will be considered a screening failure and their de-identified data will NOT be extracted or collected and their MRN will NOT be placed on the Study Subject list. All data points collected will be de-identified, containing no PHI and will be stored in Redcap. All study personnel will have access to the Redcap database.

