Subjects can withdraw from the study at any time. This withdrawal will not impact any portion of their care other than not being able to receive the study drug as it is not formulary approved at our institution. If a patient withdraws, their data will not be collected or used for analysis. Confidentiality will be maintained by using password protection for the Excel sheets, password protection for the computers used for storage of those Excel sheets, storing the sheet on the University H firewall behind the firewall and storing de-identified data within Redcap.

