13.0 REGULATORY REQUIREMENTS

13.1 INFORMED CONSENT

The patients at the top of the adult kidney transplant list awaiting DDKT maintained by UIHHSS Transplant will be used to screen for eligibility. See addendum for Eligibility Checklist. Study personnel will perform the screening. A password protected Microsoft Excel sheet will be provided by the Transplant team at UIHHSS. This sheet will have the MRN for the top patients on the kidney transplant list. If patients are initially eligible via inclusion and exclusion review, they will remain on the password protected Microsoft Excel sheet. If they are not eligible, they will be removed after screening by one of the study personnel. This password protected Microsoft Excel sheet will be maintained on the "H" drive behind the University firewall maintained by the CCTS. It is estimated that patients

will be required to be screened assuming a consent rate of ~50% and vasopressor utilization rate of ~50% of patients that receive a deceased donor kidney transplant. It is estimated that 40 subjects will be consented/enrolled in order for 20 patients to receive study drug. Twenty patients are the goal for this study and no more than 20 patients will receive study drug.

All eligible study subjects will receive a Research Letter (see addendum for Research Letter via the mail. One week after the Research Letter is mailed, the subjects will be called via telephone by study personnel to follow-up and provide any additional information regarding the study. This call is to provide information regarding the study, study enrollment criteria, and answer any questions regarding the study. This call is informational only.

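### The population is defined by need for a vasopressor but the dataset by receipt of Ang II, and withdrawn patients' data are dropped even after exposure

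*Combined protocol and SAP*

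**What the plan says.** **Population.** Section 4.1 makes perioperative distributive shock that needs a vasopressor an inclusion criterion. Section 6.0 describes the sample as "20 consecutive patients receiving DDKT requiring intraoperative or postoperative vasopressors". Both turn on need.

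**Dataset.** Three sections treat the consented patient who is not given the drug differently:
- Section 6.0, Data Management, goes by receipt: "All patients that provide informed consent but DO NOT receive Ang II (Giapreza) will be considered a screening failure". No data are extracted and no study code is assigned.
- Section 8.0 goes by need: "If a subject is enrolled and does not require Ang II (Giapreza) they will be considered a screening failure". The consequence is the same, but the same section keeps all consenting subjects on the password-protected screening list.
- Section 13.2 links a study code to every patient who is eligible and consents, whether treated or not.

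**Withdrawal.** Section 11.0 states: "If a patient withdraws, their data will not be collected or used for analysis". It makes no exception for a patient who has already received study drug.

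**Numbers.** Section 5.0: "Twenty patients are the goal for this study and no more than 20 patients will receive study drug". Section 13.1: "It is estimated that 40 subjects will be consented/enrolled in order for 20 patients to receive study drug", "assuming a consent rate of ~50% and vasopressor utilization rate of ~50% of patients that receive a deceased donor kidney transplant".

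**The concern.** Need and receipt coincide only if every consented patient who needs a vasopressor is given Ang II. When one is not, Section 6.0 makes that patient a screening failure, Section 8.0 does not address the case, and no section supplied asks which agent was used or why. Section 13.1 gives non-consenters the same label. One category therefore holds patients who declined, patients who never needed a vasopressor, and patients in the target population who did not get the study drug. Only the last group bears on whether the treated patients represent those in need, and the dataset cannot show how many there were. The claim of a consecutive series cannot be checked from it.

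The withdrawal rule is a separate matter and arguably the more serious. Safety is a stated objective (Sections 1.0 and 3.0), and the halting criteria in Section 11.0 turn on one or two events. A rule that removes an exposed patient from the data can remove an event from the safety analysis and, read literally, from the counts given to the DSMB. Because Section 5.0 caps treated patients at 20, a treated patient who withdraws cannot be replaced.

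**Working it through.** **1. The plan's own figure.** Inputs: 20 treated (Section 5.0) and about 50% vasopressor use (Section 13.1).
Consented = 20 / 0.5 = 40, which matches the stated 40. The match holds only if every consented patient in need receives Ang II.

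**2. Allowing for non-receipt.** Let q be the share of consented patients in need who never receive Ang II. The documents give no value, so q is assumed over a range.
Patients in need = 20 / (1 − q). Unseen = 20 / (1 − q) − 20. Consented = 20 / [0.5 × (1 − q)].

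| q (assumed) | In need | Unseen | Consented |
|---|---|---|---|
| 0 | 20 | 0 | 40 |
| 5% | 21.1 | about 1 | 43 |
| 10% | 22.2 | about 2 | 45 |
| 20% | 25.0 | 5 | 50 |
| 30% | 28.6 | about 9 | 58 |

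**3. What unseen patients could do to a result.** Suppose, for illustration only, that 16 of 20 treated patients (80%) reach the BP goal. With k unseen patients, the rate among all in need could lie anywhere from 16 / (20 + k) to (16 + k) / (20 + k).
- k = 5: 16/25 = 64% to 21/25 = 84%.
- k = 9: 16/29 = 55% to 25/29 = 86%.

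These are arithmetic limits. They do not say in which direction a bias would run.

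**4. Withdrawal and the halting criteria.** One criterion in Section 11.0 is met when 20% of participants have the same Grade 3 event. Read it as 20% or more, and take the review points as treated patients.
- Review at 10: 2/10 = 20%, criterion met. If one of the two withdraws and is excluded: 1/9 = 11%, not met.
- Review at 5: 1/5 = 20%, met. If that patient withdraws and is excluded: 0/4 = 0%, not met.
- Another criterion needs two participants with the same related Grade 4 event. Excluding one leaves one, and it is not met.

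**The case against.** The strongest reply is that the gap may be empty. Section 6.0 makes Ang II the first vasopressor, so using another agent instead would depart from the protocol. The same section has the investigational pharmacy hold and dispense drug for each consented transplant. The Section 8.0 wording suggests the authors had in mind only patients who never needed a vasopressor; these fail the Section 4.1 criterion, and leaving them out causes no bias. This is a pilot with a convenience sample (Section 12.0). All of this is fair and limits the size of the point. But the plan describes no means of recording such a departure, so a reader could not confirm that none occurred.

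A reader might also infer more than the documents support:
- *That consented non-receivers are erased.* Section 8.0 keeps them on a list and Section 13.2 codes them, so the number consented is recoverable. What is not collected is need, agent and reason.
- *That anyone given another vasopressor first is lost.* A patient who later receives Ang II is included, and other agents are recorded, though the listed variables do not give their order. Only those who never receive Ang II drop out.
- *That the 20 of 40 consented but untreated patients measure the bias.* Under the plan's own 50% assumption they are patients who never needed a vasopressor.
- *That the vasopressor-use rate cannot be estimated at all.* Treated over consented is available and falls short of need only through unrecorded non-receipt (for example 20/50 = 40% against 50% if q = 20%). Estimating it is not a stated objective.
- *That the losses flatter the results.* It is plausible that sicker patients get a familiar agent, or that patients with adverse events withdraw, but nothing in the documents shows either.

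The Eligibility Checklist and the consent form were not available, so a reason field or a provision on retaining data may exist there.

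**Conclusion.** The point stands in two parts.

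First, the population is defined by need and the dataset by receipt, and Sections 6.0, 8.0 and 13.2 disagree on how a consented, untreated patient is handled. The dataset therefore cannot separate no need from need without Ang II. The size is unknown: about 1 to 9 patients beside the 20 treated, resting wholly on an assumed q of 5% to 30%; the plan's own arithmetic implies zero. The direction of any bias is open.

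Second, Section 11.0 bars the use of withdrawn patients' data with no exception after exposure. With 20 treated patients at most, one such withdrawal can decide whether a halting criterion is met (2/10 against 1/9). This assumes that the rule also governs the DSMB reports, which the text does not exclude.

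A reader might think that a complete log from consent onward would by itself establish a consecutive series. It would not: about half of those approached are expected not to consent, and Section 13.1 states that non-English speakers are not pursued. Any claim has to be limited to those who consented.

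**What to change.** 1. Reconcile Sections 6.0 (Data Management), 8.0 and 13.2: one rule, stated by need or by receipt, and one point at which the study code is assigned.
2. Keep a de-identified log of every consented patient: vasopressor needed (Y/N), first agent, Ang II given (Y/N), reason if not, and withdrawal. Report it as a flow diagram. No clinical data are needed for patients who never required a vasopressor; their count is enough.
3. In Section 6.0, describe the sample as consecutive consented, English-speaking patients requiring a vasopressor if the log supports it. Otherwise drop the word consecutive.
4. Amend Section 11.0 so that, for any patient who received study drug, exposure and safety data collected up to withdrawal are retained, analysed and counted in the DSMB reports, subject to the consent form and IRB agreement.

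The cost is a tally of about 40 rows and a wording amendment to the protocol and consent form. Treatment does not change.

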7.0 EXPECTED RISKS/BENEFITS

The main anticipated benefit is the potential to establish improved hypotension management of future kidney transplant recipients at UIHHSS. This study could also potentially lead to further outcome studies on the effect vasopressors have on post-operative kidney transplant patients or studies directly comparing individual agents. Conversely, the expected risks are low given the existing data in critically ill patients with septic or other distributive shock. In the ATHOS-3 trial patients, the majority of patients evaluated were septic shock patients with a far greater severity of illness than kidney transplant recipients. In that investigation, there were no lifethreatening ADE's and minimal that were greater than placebo: most common ADE (> 4% and > 1.5 x placebo) being: thromboembolic events, thrombocytopenia, tachycardia, fungal infection, delirium, acidosis, hyperglycemia, and peripheral ischemia. With all medications, there are risks of adverse reactions. All adverse reactions that occur at an incidence of greater than 4% (and > 1.5 x placebo) in the prescribing information will be discussed individually with the subject prior to informed consent. These data points will be collected as noted above in the data collection section. There is also the risk of poorer outcomes and overall health with this agent. As with all investigations, there is a risk of breach of PHI. However, this risk is very low due to the numerous safeguards in place as described above and from using data collection in Redcap. Additionally, password protection and the hospital firewall security further reduce the likelihood of breach of information.

8.0 DATA COLLECTION AND MANAGEMENT PROCEDURES

Subjects will be screened for eligibility by the study personnel. The investigators will review a list of kidney transplant patients maintained by the Transplant Coordinators for inclusion in the study. This list will be password protected and stored on the H drive behind the University firewall on the primary investigator's password protected computer in a locked office. If a subject is not eligible after reviewing inclusion and exclusion criteria, they will be removed from this list. All subjects that provide informed consent to receive Ang II (Giapreza) will remain on this list. If a subject is enrolled and receives Ang II (Giapreza), their de-identified data will be extracted and collected in Redcap. Additionally, they will be associated with an alpha-numeric code that is linked to their medical record number (MRN) and placed on a Study Subject list. This Study Subject list will be kept in a password protected Excel file on the primary investigator's computer stored on the H drive behind the University firewall on the primary investigator's password protected computer in a locked office. It will be available only to the coinvestigators and research personnel. If a subject is enrolled and does not require Ang II (Giapreza) they will be considered a screening failure and their de-identified data will NOT be extracted or collected and their MRN will NOT be placed on the Study Subject list. All data points collected will be de-identified, containing no PHI and will be stored in Redcap. All study personnel will have access to the Redcap database.

9.0 DATA ANALYSIS

Statistical Analysis:

Continuous data -> Student t-test

Ordinal data -> Wilcoxon-Mann Whitney test

Nominal data -> Chi-square or Fisher's exact test

Multivariate regression analysis for factors associated with duration of vasopressors and worse kidney outcome

